3.2 Secondary variables

The secondary endpoints are included in a hierarchical testing sequence following the primary endpoint as ordered in Section 3.2.1 - 3.2.5.

3.2.1 The composite of CV death and hospitalization for HF

The efficacy variable is time from randomization to the first occurrence of any event in the composite of CV death and hospitalization for HF. Patients who did not have the endpoint will be censored by the same rule as for the primary endpoint.

3.2.2 Total number of (first and recurrent) hospitalizations for HF and CV death

The efficacy variable is the total number of first and recurrent hospitalizations for HF and CV death, not including urgent HF visit.

For the analysis of recurrent heart failure hospitalization and CV death, the data will be expressed in counting process style for input to the analysis as described in Section 4.2.4.1. The time from randomization to end of follow-up/censoring will be split into one or more interval with variables for start of interval, end of interval and a variable indicating if an event occurred at the end of each respective interval, or if the patient was censored. Recurrent HF hospitalizations, CV death and censoring processes all have continuous distributions so that HF hospitalization and death cannot happen at the same time. If HF hospitalization and CV death occurred at the same day, then only the CV death will be counted.

Patients who did not have the endpoint will be censored by the same rule as for the primary endpoint.

3.2.3 Change from baseline at 8 months in the KCCQ total symptom score

The efficacy variable is the change from baseline at 8 months of the Kansas City Cardiomyopathy Questionnaire (KCCQ) total symptom score (TSS). By the ITT principle, the analysis will include all data irrespective of whether the patient has discontinued study drug.

The KCCQ is a self-administered disease specific instrument for patients with HF (Green et al 2000, Spertus et al 2005). The KCCQ consists of 23 items measuring HF-related symptoms, physical limitations, social limitations, self-efficacy, and health-related quality of life. The TSS incorporates the symptom burden and symptom frequency domains into a single score. Scores are transformed to a range of 0-100. Higher scores represent a better outcome.

Baseline is defined as the value at randomization visit (visit 2). Change from baseline at each post-baseline analysis time point will be calculated as the value at the corresponding post-baseline analysis time point minus the baseline value. The KCCQ score is assessed by the patient at randomization, 4, 8, 12 months following randomization, thereafter every 12 months, and at the premature treatment discontinuation visit (PTDV) and the study closure visit (SCV).

In order to account for patients who die prior to the 8-month assessment and to accommodate non-normal distribution of KCCQ scores, a composite rank-based endpoint will be used. The values of change from baseline to 8 months in TSS of patients who survive to 8 months will be converted to ranks (across both treatment groups combined) with lower ranks attributed to worse outcomes (i.e., lower ranks corresponding to negative or smaller values of change from baseline). Patients who die prior to the 8-month assessment will be assigned the worst rank, i.e., worse than any patient surviving to 8 months, but among the deceased the relative ranking will be based on their last value of change from baseline in TSS while alive.

3.2.4 The composite of $\geq 50\%$ sustained decline in eGFR, end stage renal disease and renal death

The efficacy variable is time from randomization to the first occurrence of any event in the composite of $\geq 50\%$ sustained decline in eGFR, reaching end stage renal disease (ESRD) and renal death.

ESRD is defined as any of

- Sustained eGFR < 15 ml/min/1.73m²
- Chronic dialysis treatment
- Receiving a renal transplant

All components of the composite endpoint will be defined and described in detail in the CEA charter. The components sustained eGFR decline of $\geq 50\%$ from baseline and sustained eGFR < 15 ml/min/1.73m² will however not be adjudicated by the CEA.

Sustained eGFR decline of $\geq 50\%$ from baseline and sustained eGFR < 15 ml/min/1.73m² will be based on two consecutive central laboratory values at least 28 days apart below the respective limit. The start date of the event is the date of the first of the two qualifying consecutive central laboratory values. Thus, the analysis will include eGFR events with onset prior to PACD that are confirmed after PACD, in addition to those eGFR events confirmed prior to PACD.

Chronic dialysis will be adjudicated as treatment ongoing for at least 28 days, or when the ESRD is deemed irreversible and the dialysis treatment was stopped before day 28. Similar to the eGFR events, the onset date of chronic dialysis will be the date when the qualifying dialysis treatment started. Chronic dialysis, renal transplant and renal death will be independently adjudicated as defined in the CEA charter. Deaths adjudicated with ‘undetermined’ cause will not be considered as renal death.

Patients who do not have an endpoint event will be censored at the earliest of date of WoC and non-renal death when applicable, and otherwise at the earliest of date of last clinical event assessment and PACD. Clinical event assessment will be captured by the question for potential renal events on the eCRF event assessment page. The earliest assessment date among components will be used as the censoring date. For example, for the last clinical event assessment, if the central laboratory eGFR assessment is not done in conjunction with the assessment of dialysis and renal transplant, the date of last available central laboratory eGFR measurement will be used as the censoring date.

3.2.5 Death from any cause

The efficacy variable is time to from randomization to death from any cause. All deaths on or prior to PACD, including death after WoC will be included. Patients who are alive will be censored at the earliest of date last known alive and PACD.

Deaths occurring after WoC will not be adjudicated. For such events, the date of death will be collected only in eCRF.

3.3 Safety variables

The safety and tolerability of dapagliflozin will be evaluated from serious adverse events (SAEs), adverse events leading discontinuation (DAEs) of study drug, changes in clinical/haematology parameter and adverse events (AEs) of interest (volume depletion, renal events, major hypoglycaemic events, fractures, diabetic ketoacidosis, AEs leading to amputation and AEs leading to a risk for lower limb amputations [“preceding events”]).

SAEs will be collected from time of informed consent until and including the patient’s last visit.

Non-serious AEs will be collected from randomization until and including the patient’s last visit, only if it is a DAE, an AE of interest, an AE leading to a potential endpoint or the AE is the reason for interruption of study drug or dose reduction.

Deaths and HF events will be recorded as SAEs in the database, but will not be reported to health authorities to avoid unnecessary unblinding of efficacy endpoints that are fulfilling the SAE criteria. If it is determined by the CEA committee that a potential endpoint does not meet the endpoint criteria, but is judged by investigators to fulfil the SAE criteria, then the event will be reported to AZ patient safety data entry site and if applicable to the health authorities.

4. ANALYSIS METHODS

4.1 General principles

No multiplicity adjustment will be made to confidence intervals as they will be interpreted descriptively and used as a measure of precision. All p-values will be unadjusted. P-values for variables not included in the confirmatory testing sequence, or following a non-significant test in the sequence will be regarded as nominal.

The primary and secondary analyses include adjudicated events occurring on or prior to PACD.

Stratification of analyses for T2D status will be performed using the stratification values as entered in IxRS to determine the randomization assignment.

Baseline diabetic status

T2D at baseline will be defined as established diagnosis of T2D (recorded in eCRF medical history) or central laboratory HbA1c $\geq 6.5\%$ at both visit 1 (enrollment) and visit 2 (randomisation).

Exploratory analyses may include “pre-diabetic” subjects not categorized as T2D above and having central laboratory HbA1c $\geq 5.7\%$ at visit 1 and/or visit 2. Other subjects will be categorized to a third group, here denoted “normo-glycaemic”

In consideration of missing data, subjects without medical history of T2D and a single HbA1c $\geq 5.7\%$ (including $\geq 6.5\%$) from visit 1 or visit 2 will be categorized as pre-diabetic. Subjects without medical history of T2D and no HbA1c measurement or a single measurement $< 5.7\%$ will be included in the normo-glycaemic group (thus non-diabetic).

Incomplete dates

All efforts should be made to obtain complete dates of clinical assessments and events. For analyses requiring complete dates, partially missing dates will be imputed based on available corroborating information. Absent of any additional corroborating information, partially missing dates will be imputed as follows: if only the year part of a date is available (YY), then the date will be set to YY0701. If only the year and month is available (YYMM), then the date will be set to YYMM15. Additional imputation rules will be defined as appropriate to ensure that eg, dates will not be imputed as prior to randomization, after death or end date before start date.

Baseline laboratory value

For all laboratory variables, with the exception of eGFR, the baseline value is defined as the last value on or prior to date of first dose of randomized study drug, or for patients who did not receive treatment, the last value on or prior to date of randomization.

eGFR

The eGFR values will be calculated (in mL/min/1.73 m²) from the central laboratory creatinine measurements using the CKD-EPI formula (Levey et al 2009). Descriptive statistics will be presented based on laboratory data.

Baseline eGFR will be calculate as mean of visit 1 and visit 2 values. In case of re-screening, the mean of latest values at each of visit 1 and visit 2 on or prior to date of randomization will be used.

Study drug compliance

The percentage of study drug compliance for the overall treatment period will be derived for each patient based on pill counts as the number of pills taken (dispensed – returned), relative to the expected number of pills taken. The expected number of pills taken is defined as $1 * (\text{date of last dose} - \text{date of first dose} + 1)$, excluding days of interruption.

Study drug compliance will be presented descriptively, including mean, median, quartiles and 5% and 95% percentiles.

4.1.1 Estimand for primary and secondary outcomes

The primary and secondary event based objectives will be evaluated under the treatment policy estimand to reflect the effect of the initially assigned randomized study drug, irrespective of adherence to randomized study treatment. Specifically, the analysis will be performed for the full analysis set including all events that occurred on or prior to PACD, including events following premature discontinuation of study drug.

The estimand for the change from baseline in KCCQ total symptom score at 8 months will employ a combination of a treatment policy strategy and a composite strategy. For the intercurrent event of death (due to any cause) prior to the KCCQ assessment at 8 months, a composite strategy will be used, where death will be considered unfavorable and represented by a lowest (worst) rank of a combined outcome variable as described in Section 3.2.3. For all other types of intercurrent events, including but not limited to a premature discontinuation of randomized treatment, a treatment policy strategy will be used.

4.1.2 Hypotheses

To control the overall type I error rate at 2.5% one-sided, the significance level will be adjusted for one interim analysis of efficacy performed by the DMC (Section 5). For the

primary endpoint the following null hypothesis will be tested at the 2.496% one-sided significance level

$$H_0: \text{HR [dapagliflozin:placebo]} \geq 1$$

versus the alternative hypothesis

$$H_1: \text{HR [dapagliflozin:placebo]} < 1$$

The secondary endpoints included in confirmatory statistical testing using a closed testing procedure (Section 4.1.3) will be based on similar one-sided alternative hypotheses for the respective treatment difference. The significance level will be re-calculated based on the exact proportion of primary endpoints included in the interim analysis and may be marginally adjusted (Section 5).

4.1.3 Confirmatory testing procedure

A closed testing procedure including a pre-specified hierarchical order of the primary and secondary endpoints will be utilized. The Type I error will be controlled at a one-sided 0.02496 level for multiplicity across primary and secondary endpoints and in consideration of the planned interim analysis. Statistical significance will be assessed in the pre-specified order of the endpoints as specified in Section 1.1.1 and 1.1.2. The testing procedure will continue down the hierarchy if the preceding endpoint is rejected at a one-sided 0.02496 level and will stop if the null hypothesis for the preceding endpoint is not rejected at a one-sided 0.02496 level.

If the study is stopped in the efficacy interim analysis (Section 5), testing of secondary endpoints will continue down the hierarchy at one-sided significance level 0.001.

4.1.4 Presentation of time-to-event analyses

In general, summary tables of time-to-event analyses will include the number and percent of patients with event per treatment group, event rate, hazard ratio with 95% confidence interval and p-value. The event rate will be derived as the number of patients with event divided by the total duration of follow-up across all patients in a given group, presented as patients with event per 100 patient years.

Kaplan- Meier (KM) estimates of the cumulative proportion of patients with events will be calculated and plotted per treatment group, with the number of patients at risk indicated below the plot at specific time points. The KM plots will be presented for all time to event analyses, including the individual components of the composite endpoints.

4.1.5 Vital status and follow-up of endpoints

Potential endpoints will be collected and adjudicated from randomization throughout the study until and including the patient's last visit. The investigator will attempt to collect vital status (dead or alive) at the end of the study for all patients, including vital status from publicly

available sources for patients who have withdrawn consent, in compliance with local privacy laws/practices.

Known vital status at the end of the study will be defined when the patient is dead or has date last know alive (derived from the eCRF final status form) on or after the PACD. In patient disposition the number of patients who are dead, alive or with unknown vital status will be reported separately for patients who did/did not withdraw consent. The term lost to follow-up (LTFU) will be limited to only patients with unknown vital status.

Follow-up of the primary endpoint will be defined in terms of completion of the event assessment question for a potential HF event as described for censoring in Section 3.1. Thus a patient that is not LTFU, ie with known vital status, may have incomplete follow-up of endpoints.

Complete follow up of the primary endpoint will be defined as the patient had a primary endpoint event, died from non-CV death or had complete event assessment on or after the PACD.

In addition to the number and percent of patients with complete follow-up, the proportion of total patient time with complete follow-up will be reported per treatment group.

Patient time with complete follow-up will be defined as time from randomization until the earliest of first primary endpoint event, death, WoC, censoring due to incomplete event assessment (in cases where last complete event assessment is prior to PACD) or PACD. The denominator, representing maximum complete follow-up, will be the time to first primary endpoint event, death or PACD.

4.2 Analysis methods

4.2.1 Demographics and baseline characteristics

Demographic and baseline characteristics, including medical history, will be summarized, using frequency distributions and summary statistics based on the FAS data set, for each treatment group as well as for all patients combined. No statistical test will be performed for comparison of any baseline measurement among treatment groups.

4.2.2 Concomitant and baseline medication

Baseline medication is defined as medication with at least one dose taken before date of randomization and with no stop date before date of randomization.

Concomitant medication is defined as medications taken post randomization, irrespective of study drug.

The frequency of baseline and concomitant medication will be presented for the FAS per ATC class and treatment group.

Summaries of prohibited medication (as defined in CSP Section 7.7.1) will be presented. In this study prohibited medication is limited to open label SGLT2 inhibitors taken in combination with IP.

4.2.3 Analysis of the primary efficacy variable

The primary variable is the time to first event included in the primary composite endpoint. The primary analysis will be based on the ITT principle using the FAS, including events with onset on or prior to PACD, adjudicated and confirmed by the CEA committee.

In the analysis of the primary composite endpoint, treatments (dapagliflozin versus placebo) will be compared using a Cox proportional hazards model with a factor for treatment group, stratified by T2D status at randomization, and adjusting for history of hospitalization for heart failure. The analysis will use WoC, non-CV death, last clinical event assessment and PACD for censoring of patients without any primary event as described in Section 3.1. The Efron method for ties and p-value based on the score statistic will be used. The event rates, p-value, HR, and 95% confidence interval will be reported.

The contribution of each component of the primary composite endpoint to the overall treatment effect will be examined. In the analysis of the components, all first event of the given type will be included irrespective of any preceding non-fatal composite event of a different type. Consequently, the sum of the number of patients with events in the component analysis will be larger than the number of patients with composite events. Methods similar to those described for the primary analysis will be used to separately analyze the time from randomization to the first occurrence of each component of the primary composite endpoint.

Kaplan-Meier estimates of the cumulative proportion of patients with event will be calculated and plotted, for the composite endpoint and for the individual components.

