1.4 Number of patients

The primary objective of the study is to determine the superiority of dapagliflozin versus placebo in reducing the incidence of the primary composite endpoint. Assuming a true hazard ratio (HR) of 0.80 between dapagliflozin and placebo, using a one-sided alpha of 2.5%, 844 primary endpoint events will provide a statistical power of 90% for the test of the primary composite endpoint. This is based on an overall 1:1 allocation between dapagliflozin and placebo. The study is event-driven. The assumed HR of 0.80 is considered as clinically relevant and has taken into account the HF outcomes in the EMPA-REG trial (Fitchett et al 2016).

With an annual event rate of 11% in the placebo treatment group, 4500 patients are estimated to provide the required number of primary events, based on an anticipated recruitment period of 18 months and an average follow-up period of approximately 24 months. The assumed placebo event rate of 11% is based on a review of recently published clinical studies in the HFrEF population, including the PARADIGM-HF trial (McMurray et al 2014). The number of patients with incomplete follow-up of endpoints is expected to be small; hence, these are not considered in the determination of the sample size.

This study is a group sequential design study with one interim analysis at 75% of the adjudicated target number of events using Haybittle-Peto boundary (a one-sided alpha=0.001), leaving a one-sided alpha of 2.496% for the final analysis.

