4.2.3.1 Subgroup analysis of the primary endpoint

Exploratory subgroup analyses of the primary composite endpoint will be performed for the characteristics listed in Table 1. A test of interaction between randomized treatment group and the subgroup variable will be performed in each Cox model, stratified by T2D and including as covariates history of hospitalization for HF, the relevant subgroup variable and the interaction between treatment and the subgroup variable. In addition to the number and percent of patients with event, event rate estimate, HR with 95% confidence interval and p-value for each subgroup, the interaction p-value will be presented. HRs with confidence interval will be presented in a forest plot, also including the event rate and interaction p-value. The p-values for the subgroup analyses and interaction will not be adjusted for multiple comparisons as the tests are exploratory and will be interpreted descriptively.

Table 1 Characteristics and categories for sub group analysis of the primary endpoint

Characteristic	Categories
Age (years)	<= 65, >65
Sex	Male, female
Race	White, Black or African, Asian, Other
Geographic region	Asia (China, India, Japan, Taiwan, Vietnam) Europe (Bulgaria, Czech Republic, Denmark, Germany, Hungary, Netherlands, Poland, Russia, Slovakia, Sweden, UK) North America (Canada, US) South America (Argentina, Brazil)
NYHA class at enrollment	II, III/IV
LVEF at enrollment	<= median, > median
NT-proBNP at enrollment	<= median, > median
Prior Hospitalization for HF	Yes, No
MRAs at baseline	Yes, No
Type 2 diabetes at baseline *	Yes, No
Atrial fibrillation or flutter at enrolment ECG	Yes, No
Etiology of HF	Ischemic, Non-ischemic/unknown
BMI (kg/m ²) at enrollment	<30, ≥30
Baseline eGFR (ml/min/1.73m ²)	<60, ≥60

* Defined as history of T2D or HbA1c ≥6.5% at both visit 1 and visit 2 (Section 4.1) The subgroup analysis by T2D status will exclude T2D as a stratification factor from the model.

The subgroup analyses will be repeated for the CV death component of the primary composite endpoint and the secondary composite endpoint of CV death or HF hospitalization.

No hazard ratio estimates with confidence interval and p-values will be given for subgroups with less than 15 events in total, both treatment groups combined.

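### The primary Cox model is valid; adding continuous log NT-proBNP, already collected at enrolment, would be a cheap and modest gain in power

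*SAP*

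**What the plan says.** Section 4.2.3 compares treatments with a Cox model "stratified by T2D status at randomization, and adjusting for history of hospitalization for heart failure", using Efron ties and a score-test p-value. Section 4.2.4 uses the same stratification and covariate for the composite of CV death or HF hospitalization.

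Table 1 in section 4.2.3.1 lists "NT-proBNP at enrollment" as one of 14 subgroup characteristics, divided at the median. It enters a Cox model only there, with its treatment interaction, and that analysis is exploratory.

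Section 1.4 states that "844 primary endpoint events will provide a statistical power of 90% for the test of the primary composite endpoint" under a hazard ratio of 0.80, with 1:1 allocation and a one-sided alpha of 2.5%. The interim analysis at 75% of events is described as "leaving a one-sided alpha of 2.496% for the final analysis". The calculation mentions no covariates. The SAP gives no reason for the choice of covariate and does not say how strongly NT-proBNP predicts the primary endpoint.

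**The concern.** Leaving a prognostic baseline variable out of a Cox model pulls the treatment log hazard ratio towards zero without a matching fall in its standard error, so the test loses some power. Pre-specified adjustment recovers that power, allows for chance imbalance in the covariate and does not inflate type I error.

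The SAP does this for other endpoints. The renal composite is adjusted for baseline eGFR (section 4.2.4) and the KCCQ test for baseline TSS (section 4.2.4.2). The HF endpoints are adjusted only for a binary history.

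The design has little margin, because 844 events give 90% power and no more. Under section 4.1.3, a non-significant primary test ends confirmatory testing of all five secondary endpoints.

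**Working it through.** **Step 1: reproduce the plan's figure.** Inputs from section 1.4: HR 0.80, one-sided alpha 0.025, power 90%, 1:1 allocation.

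- Events (Schoenfeld) = 4(z₀.₀₂₅ + z₀.₁₀)² / (ln 0.80)² = 4(1.960 + 1.282)² / 0.2231² ≈ 844.1. This agrees with the stated 844 (845 if rounded up).
- Power at 844 events = Φ(√844/2 × 0.2231 − 1.960) = Φ(1.281) = 90.0%. At alpha 0.02496 it is still 90.0% to one decimal.
- The final alpha, with 0.001 used at 75% information, recomputes to 0.02496.

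**Step 2: set up the comparison.** Trials were simulated with 4500 patients, uniform accrual over 18 months, an 11% annual placebo risk, no dropout and a stop at the 844th event. Reading 11% as an annual risk fits section 1.4: with hazard −ln 0.89 = 0.1165 and 24 months of follow-up, 2250(1 − e^−0.2331) + 2250(1 − e^−0.1864) ≈ 851 events. Both models were fitted to the same simulated trials with the T2D-stratified score test at one-sided 0.02496.

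Assumptions not taken from the SAP:
- prior HF hospitalization in 47% of patients, with HR 1.4;
- T2D in 45%;
- log NT-proBNP normally distributed and independent of prior HF hospitalization;
- the hazard ratio per SD of log NT-proBNP, varied over a range.

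**Step 3: planned-model HR held at about 0.80** (3000 trials per row, Monte Carlo SE of each power about 0.5 to 0.6 points).

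| Assumed HR per SD | HR, planned model | HR with NT-proBNP | Power, planned | Power with NT-proBNP | Gain (points) |
|---|---|---|---|---|---|
| 1.3 | 0.7990 | 0.7977 | 90.1% | 90.7% | 0.5 |
| 1.6 | 0.7999 | 0.7953 | 89.9% | 91.2% | 1.4 |
| 2.0 | 0.7994 | 0.7885 | 90.8% | 93.6% | 2.8 |
| 2.5 | 0.8001 | 0.7810 | 90.0% | 94.9% | 4.9 |

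Gains are taken before rounding. As a cross-check, Φ(√844/2 × |ln HR| − 1.9606) at the adjusted HRs gives 90.7%, 91.4%, 93.2% and 94.8%.

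**Step 4: no prognostic effect.** With a hazard ratio per SD of 1.0, power was 89.2% for the planned model and 89.1% with NT-proBNP added (1500 trials). The extra covariate costs essentially nothing.

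**Step 5: the other reading of 0.80.** Section 1.4 does not say whether 0.80 is conditional on covariates. If 0.80 is the HR given NT-proBNP, the planned model has 89.1%, 87.0%, 84.5% and 81.3% power for 1.3, 1.6, 2.0 and 2.5 per SD. Adding NT-proBNP gives 89.7%, 89.1%, 88.2% and 89.7% (1500 trials per row, SE about 0.8 to 1.0 points).

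**The case against.** The strongest objection is that nothing here is wrong. The model is fully pre-specified and valid, and the stated power needs no help from a further covariate. That stands, and it makes this an optional improvement.

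Second, the SAP never says that NT-proBNP is prognostic, and nothing in it ranks NT-proBNP above the other 13 characteristics in Table 1. This also stands. The size of the gain is therefore conditional on an assumed strength, and correlation with prior HF hospitalization would reduce it.

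Third, the change would come late. SAP version 3.0 is dated July 2019, and Table 4 already tabulates blinded 8-month data for 3883 patients (255 + 402 + 831 + 1522 + 561 + 223 + 89). The design also has an interim test at about 75% of events. If that test has been run under the current model, a change would leave interim and final statistics from different models. The SAP does not say whether it has been run. This limits how the change can be made but does not make an adjusted model invalid if it is fixed before unblinding.

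A reader might infer from step 5 that the trial is underpowered. The documents do not support that: the stated 90% reproduces, and the lower figures need both a conditional reading of 0.80 and an assumed NT-proBNP effect. A reader might also call the gain free, or say that the model ignores everything but prior HF hospitalization. Neither holds. The model is also stratified by T2D, the adjusted HR answers a slightly different conditional question, and extra rules would have to be written down.

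**Conclusion.** The primary analysis is sound as planned. Adding continuous log NT-proBNP is a worthwhile but small efficiency gain: about 0.5 to 3 power points for an assumed hazard ratio per SD of 1.3 to 2.0, and about 5 points only at 2.5. This takes the planned-model HR as 0.80 and NT-proBNP as independent of prior HF hospitalization. With no prognostic effect, the gain is nil and so is the loss. Confidence in the direction is good. Confidence in the size is low, because the SAP supplies no prognostic strength. The model for CV death or HF hospitalization uses the same stratification and covariate, so the same reasoning applies to it, although its gain was not simulated.

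**What to change.** If the interim analysis has not been run, amend sections 4.2.3 and 4.2.4 before unblinding:

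- Add log NT-proBNP at enrolment as a continuous covariate to the primary model and to the model for CV death or HF hospitalization. Leave the T2D stratification, prior HF hospitalization, Efron ties and score test unchanged.
- Replace any missing NT-proBNP value with the overall median across both arms.
- State that the same model is used at the interim and final analyses.
- Keep the current model as a sensitivity analysis and report both HRs.

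If the interim has already been run under the current model, leave the primary model alone and pre-specify the NT-proBNP-adjusted model as a supportive analysis. That would address chance imbalance in NT-proBNP but would not raise the power of the primary test.

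The cost is SAP wording and one covariate, with no new data. The downside is that the adjusted HR is conditional on NT-proBNP and slightly further from 1 (0.789 to 0.798 in the simulations for 1.3 to 2.0 per SD, against 0.80), so the report must explain the two figures.
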